4.2.3 Sensitivity Analyses

A sensitivity analysis will be performed with respect to imputation related to the following intercurrent event to assess the robustness of the analysis with regard to missing data:

- Discontinuation of treatment due to reasons not related to lack of efficacy (including Covid-19 related reasons): At Day 56 (Visit 6) or later: imputation of response information (hypothetical strategy)
- Missing Day 84 (Visit 7) EASI assessment imputation of response information using data from Day 56 (Visit 6) or later (hypothetical strategy), if none of the conditions applies which are described above

As a "worst case" scenario the primary analysis (according to primary estimand) will be repeated by imputing the missing EASI 75 response information at Day 84 (Visit 7) as non-response (instead of using the multiple imputation with the logistic regression model).

Furthermore, the primary analysis (according to primary estimand) will be repeated by imputing the missing EASI 75 response information at Day 84 (Visit 7) using last observation carried forward (instead of using the multiple imputation with the logistic regression model) (refer to Section 8.4.2 for details). EASI scores will only be carried forward if no rescue medication was used within the last 7 days before the EASI score to avoid influence of EASI scores directly after rescue medication on the imputation of the primary endpoint.

4.2.4 Supplementary Analyses

Handling of use of rescue medication

The following supplementary analyses will be performed on the PPS to further assess the influence of rescue medication use on the EASI 75 response.

The analysis will be performed with a different handling of the following intercurrent event:

• Use of topical rescue medication: At Day 56 (Visit 6) or later (until Day 84 (Visit 7) or end of treatment if before Day 84 (Visit 7)): analyze study participant as non-responder (composite strategy)

Before Day 56 (Visit 6): disregard use of topical rescue medication (treatment policy strategy)

Use of rescue medication will be handled for supplementary analyses as outlined in the following:

The study participant is considered a non-responder in case of rescue medication use between the EOT visit and

- Baseline,
- 2 weeks after baseline,
- 4 weeks after baseline.

One additional analysis will be performed where rescue medication does not trigger the classification as non-responder at all to assess the effect of combined treatment of zabedosertib with topical AD medication.

If rescue medication does not trigger the classification as non-responder, the EASI 75 response will be based on the EASI scores collected after use of rescue medication.

Participants who take SoC medication or who discontinue study intervention due to lack of efficacy will still be counted as a non-responder for the time points after SoC use or discontinuation of study intervention due to lack of efficacy as described above.

The EASI score at time points after discontinuation of treatment due to other reasons not related to lack of efficacy or otherwise missing values will be imputed using "worst case" and last observation carried forward as described in Section 4.2.3. No multiple imputation approach using logistic regression will be performed for the supplementary analysis due to potential scarceness of participants continuing until Day 56 (Visit 6) without any rescue medication.

All other intercurrent events will be handled as described for the primary estimand.

Analysis on FAS

The EASI 75 response will be analyzed on the FAS according to the supplementary estimand (refer to Section 1.1). Imputation techniques in case of missing EASI 75 response information at Day 84 (Visit 7) will be as for the primary analysis.

However, the missing EASI 75 response information at Day 84 (Visit 7) due to other reasons not related to lack of efficacy will only be imputed as non-response as well as using last

observation carried forward as described in Section 4.2.3. No multiple imputation approach using logistic regression will be performed to impute EASI score at Day 84 (Visit 7) for the FAS due to potential scarceness of participants without use of rescue medication in the 7 days before EASI scores at early time points before Day 56 (Visit 6).

The supplementary analyses with respect to use of rescue medication as outlined above will not be performed on the FAS with exception of the following:

The analyses on the FAS as described above will be repeated with rescue medication use triggering the classification of non-response for all subsequent visits irrespectively of the time of rescue medication use (i. e. starting from Day 1 (Visit 1) until Day 84 (Visit 7) or end of treatment.

Table 4-1 summarizes the analyses for the primary endpoint EASI 75 response at Day 84 (Visit 7):

Analysis set	Analysis type	After "Use of rescue medication"	After "Use of SoC" / "discontinuation due to lack of efficacy"	After "Discontinua- tion due to other reasons" or missing values	No. of binary analysis
PPS	Primary	Non- response at/after Day 56 (Visit 6)	Non-response	Multiple imputation using logistic regression	B_1.1 (Primary)
	Sensitivity	Non- response at/after Day 56 (Visit 6)	Non-response	Non-response	B_1.2 (Sensiti- vity 1.1)
				Last observation carried forward	B_1.3 (Sensiti- vity 1.2)
	Supplementary	Non- response after Day 1 (Visit 3)	Non-response	Non-response	B_2.1 (Supple- mentary 1.1)

Table 4-1: Primary, sensitivity and supplementary analyses for the primary endpoint EASI 75 response at Day 84 (Visit 7)

Page: 23 of 72

				Last observation carried forward	B_2.2 (Supple- mentary1 .2)
		Non- response at/after Day 14 (Visit 4)	Non-response	Non-response	B_3.1 (Supple- mentary 2.1)
				Last observation carried forward	B_3.2 (Supple- mentary 2.2)
		Non- response at/after Day 28 (Visit 5)	Non-response	Non-response	B_4.1 (Supple- mentary 3.1)
				Last observation carried forward	B_4.2 (Supple- mentary 3.2)
		Not considered as non-response at any time	Non-response	Non-response	B_5.1 (Supple- mentary 4.1)
				Last observation carried forward	B_5.2 (Supple- mentary 4.2)
FAS	Supplementary	Non- response at/after Day 56 (Visit 6)	Non-response	Non-response	B_6.1 (Supple- mentary 5.1)

Version 1.0

		Last observation carried forward	B_6.2 (Supple- mentary 5.2)
Non- response after Day 1 (Visit 3)	Non-response	Non-response	B_7.1 (Supple- mentary 6.1)
		Last observation carried forward	B_7.2 (Supple- mentary 6.2)

4.3 Secondary Endpoint(s) Analysis

4.3.1 Key Secondary Endpoint(s)

Not applicable.

4.3.2 Supportive Secondary Endpoint(s)

Calculation of the weekly average of Peak Pruritus 0-10 NRS

The weekly average of the Peak Pruritus 0-10 NRS will be evaluated in a visit-based manner, in order to enable an analysis comparable to the ClinROs:

The daily Peak Pruritus score at the 7 days preceding the visit will be averaged (arithmetic mean) if at least 4 scores are present in the respective time frame. Otherwise, the weekly Peak Pruritus 0-10 NRS will be missing for the respective visit. For end of treatment visits no scores after end of treatment will be considered for the average.

Daily recording of Peak Pruritus 0-10 NRS in the follow-up phase was not possible after Day 23 after end of treatment for many participants due to a technical issue. In this case the recording ended before the planned FU visit at Day 28 after end of treatment. Due to this reason, the weekly Peak Pruritus 0-10 NRS for the FU visit will not be based on the 7 days preceding the FU visit but it will be based on the recording from Day 17 to Day 23 after end of treatment for all participants. Thus, the FU assessment for the weekly Peak Pruritus 0-10 NRS will be a bit earlier than that for the other efficacy assessments.

The following will be considered for imputation procedures: Weekly average Peak Pruritus 0-10 NRS scores will only be used for multiple imputation or be carried forward as described in Section 4.2 and 4.3 if the respective visit was at least 7 days after last rescue medication use

(i.e. no rescue medication use during the last 7 days before the visit when the daily Peak Pruritus scores are assessed which are considered for the weekly average. If this is not possible then an earlier weekly average score will be used for imputation, the baseline weekly average score will always be acceptable.

Binary endpoints

For binary endpoints, the secondary efficacy analysis will use the same approach as for the primary analysis (including sensitivity and supplementary analyses).

- In detail, the proportion of participants reaching EASI 50 response at Week 12 (Day 84) will be analyzed. An EASI 50 response is defined as achievement of 50% reduction from baseline in the Eczema Area and Severity Index.
- Likewise, the proportion of participants reaching EASI 90 response at Week 12 (Day 84) will be analyzed. An EASI 90 response is defined as achievement of 90% reduction from baseline in the Eczema Area and Severity Index.
- Furthermore, the proportion of participants with a response with respect to vIGA-AD at Week 12 (Day 84) will be analyzed. A vIGA-AD response refers to achievement of a vIGA-AD of 0 or 1 with at least a 2-grade reduction from baseline (vIGA-AD scale ranges from 0-4).
- In addition, the proportion of participants with a response with respect to the average of the Peak Pruritus 0-10 NRS at Week 12 (Day 84) will be analyzed. A response with respect to peak pruritus will be defined as achievement of a ≥4 point improvement (reduction) in the weekly average of the Peak Pruritus 0-10 NRS score from baseline (for participants with Peak Pruritus 0-10 NRS score ≥ 4 at baseline) (Phan et al, 2012).

The logistic regression model used for imputation (Section 4.2.2) will include the EASI score, vIGA-AD score or the weekly average Peak Pruritus 0-10 NRS at baseline and Day 56 (Visit 6), respectively (if possible).

Continuous endpoints

For continuous endpoints, i.e. percent change from baseline in EASI score, absolute change from baseline in BSA as well as percent change from baseline in the weekly average of the Peak Pruritus 0-10 NRS score, the impact of a potential use of rescue treatment or SoC for treatment of AD on the efficacy will be accounted for as follows:

If rescue medication is used between Day 56 (Visit 6) and Day 84 (Visit 7) (or end of treatment if before Day 84 (Visit 7)) or if SoC is used (at any time) or study drug is discontinued due to lack of efficacy (at any time), data collected afterwards will be handled as missing.

Missing data will be imputed using a multiple imputation approach followed by an analysis of covariance model.

Imputation of missing EASI score for Day 84 (Visit 7)

The multiple imputation procedure for continuous endpoins will be similar to the one for binary endpoints but using linear regression instead of logistic regression. For a detailed technical description and data handling steps of the imputation of missing EASI score please also refer to Section 8.4.1 and 8.4.3. In the following the imputation procedure will be described in general:

The following analyses will be performed on the PPS:

In a first step any values (set to) missing after rescue medication use at or after Day 56 (Visit 6), i.e until Day 84 (Visit 7) or end of treatment if before Day 84 (Visit 7), after use of systemic SoC and after discontinuation of study intervention due to lack of efficacy will be imputed by carrying forward the worst observed post-dose value to impute the value at Day 84 (Visit 7) (refer to Section 8.4.3). SoC medication use after early discontinuation due to other reasons will not trigger the imputation by worst observed post-dose value carried forward for the following time points.

The remaining missing values at Day 84 (Visit 7) will be imputed using a multiple imputation procedure based on the absolute values of the EASI score.

The imputation will be performed by treatment group using the monotone linear regression method from the SAS multiple imputation procedure (PROC MI).

For a participant

- with EASI score at baseline and Day 56 (Visit 6),
- without EASI score at Day 84 (Visit 7),
- without systemic SoC use before Day 56 (Visit 6) EASI score,
- without rescue medication use at Day 56 (Visit 6) EASI score

a linear regression model will be built based on the following participants:

- with EASI score at baseline and Day 56 (Visit 6),
- with EASI score at Day 84 (Visit 7),
- without systemic SoC use before Day 56 (Visit 6) EASI score,
- without rescue medication use at Day 56 (Visit 6) EASI score,
- without rescue medication use (irrespectively of the indication) within the 7 days before the Day 56 (Visit 6) EASI score (to avoid influence of EASI scores directly after rescue medication on the imputation of the value at Day 84 (Visit 7)).

Participants with use of systemic SoC or rescue medication or discontinuation of study intervention due to lack of efficacy after the Day 56 (Visit 6) EASI score and until Day 84 (Visit 7) will have an EASI score (worst post dose observation) at Day 84 (Visit 7) and can be included in the linear regression model if they fulfill the criteria specified above.

The EASI score at Day 84 (Visit 7) will be the dependent variable in the linear regression model and the following variables will be included as independent variables:

- EASI score at baseline,
- EASI score at Day 56 (Visit 6).

If the multiple imputation using linear regression as described above is based on less than 8 participants per treatment group the baseline EASI score and the EASI score at the previous visit will be used as independent variable in the linear regression model as described above. If there will not be sufficient participants to include one of the post-dose visits (Day 28 (Visit 5),

or – if not possible – Day 14 (Visit 4)) the linear regression model will only use the EASI score at baseline as independent variable. Then the model will be based on all participants with EASI score at baseline and EASI score at Day 84 (Visit 7). The EASI at Day 84 (Visit 7) could be imputed using worst post-dose observation carried forward after SoC use, discontinuation of study intervention due to lack of efficacy or use of rescue medication after Day 56 (Visit 6). The variables used in the regression model will be indicated below the output table.

If there is a participant with rescue medication use within the 7 days before the Day 56 (Visit 6) EASI score and missing EASI at Day 84 (Visit 7) which needs to be imputed the same procedure as described above (in case of less than 8 participants per treatment group) will be applied for that participant.

Imputed values below the minimum (0) or above the maximum (72) possible EASI score will be set to the minimum or maximum score.

Imputation according to the procedure defined above will be performed 50 times. All participants with EASI scores imputed using the linear regression method will be combined with the remaining participants (which will have the same values for each imputed dataset).

Then an analysis of covariance (ANCOVA) with the percent change from baseline in the EASI score at Day 84 (Visit 7) as dependent variable will be applied for each imputed dataset. The model will include treatment group as fixed effect and the EASI baseline value as covariate. The results from the model will be combined by Rubin's rule using SAS MIANALYZE procedure. The treatment difference (including 95% confidence intervals) at Day 84 (Visit 7) will be presented.

As a "worst case" scenario the analysis will be repeated by imputing all missing EASI scores at Day 84 (Visit 7) by carrying forward the worst post-dose EASI score (refer to Section 8.4.3 for details).

Furthermore, the analysis will be repeated by imputing all missing EASI scores at Day 84 (Visit 7) using last observation carried forward (refer to Section 8.4.3 for details).

As for the binary endpoints supplementary analyses with respect to the time point after which rescue medication use leads to setting the subsequent values to missing will be performed as described for the binary endpoints in Section 4.2.4. The analysis will be similar to the main analysis but considering rescue medication use for analysis starting from Day 1 (Visit 3) or not at all. These analyses handle the rescue medication use in a similar manner over time. Thus, a mixed effect repeated measurement model will be applied in addition assuming the values are missing at random; and furthermore multiple imputation based on linear regression including all participants will be performed with subsequent ANCOVA analysis (for details refer to Section 4.4.2 and 8.4.3).

The analyses described above will be repeated on the FAS with exception of the main analysis (see Table 4-2). This approach will not be applied due to potential scarceness of participants without use of rescue medication in the 7 days before EASI scores at early time points before Day 56 (Visit 6). Furthermore, the analysis disregarding the use of rescue medication will not be performed on the FAS.

Table 4-2 summarizes the analyses for the percent change in EASI score at Day 84 (Visit 7).

Table 4-2 Main, sensitivity and supplementary analyses for the secondary endpoint percent change from baseline in EASI at Day 84 (Visit 7)

Analysis set	Analysis type	After "Use of rescue medication"	After "Use of SoC / discontinuation due to lack of efficacy"	After "Discontinuatio n due to other reasons" or missing values	No. of analysis for continuo us endpoint
	Main	Worst post- dose observation carried forward at/after Day 56 (Visit 6)	Worst post-dose observation carried forward	Multiple imputation using linear regression	C_1.1 (Main)
	Sensitivity	Worst post- dose observation carried forward at/after Day 56 (Visit 6)	Worst post-dose observation carried forward	Worst post-dose observation carried forward	C_1.2 (Sensiti- vity 1.1)
		Last observation carried forward at/after Day 56 (Visit 6)	Last observation carried forward	Last observation carried forward	C_1.3 (Sensiti- vity 1.2)
	Supplemen tary	Worst post- dose observation carried forward after Day 1 (Visit 3)	Worst post-dose observation carried forward	Worst post-dose observation carried forward	C_2.1 (Supple- mentary 1.1)
		Last observation carried forward after	Last observation carried forward	Last observation carried forward	C_2.2 (Supple- mentary 1.2)

CONFIDENTIAL

Statistical Analysis Plan BAY 1834845 / 22158 Version 1.0

Page: 29 of 72

		Day 1 (Visit 3)			
	Values set to missing after Day 1 (Visit 3), no imputation	Values set to missing after SoC, no imputation	No imputation	C_2.3* (Supple- mentary 1.3)	
	Multiple imputation using linear regression after Day 1 (visit 3)	Multiple imputation using linear regression	Multiple imputation using linear regression	C_2.4 (Supplem entary 1.4)	
		Disregard use of rescue medication for analysis	Worst post-dose observation carried forward	Worst post-dose observation carried forward	C_3.1 (Supple- mentary 2.1)
			Last observation carried forward	Last observation carried forward	C_3.2 (Supple- mentary 2.2)
			Values set to missing after SoC, no imputation	No imputation	C_3.3* (Supple- mentary 2.3)
			Multiple imputation using linear regression	Multiple imputation using linear regression	C_3.4 (Supple- mentary 2.4)
FAS	Supplemen tary	Worst post- dose observation carried forward at/after Day 56 (Visit 6)	Worst post-dose observation carried forward	Worst post-dose observation carried forward	C_4.1 (Supple- mentary 3.1)

CONFIDENTIAL

Page: 30 of 72

Last observation carried forward at/after Day 56 (Visit 6)	Last observation carried forward	Last observation carried forward	C_4.2 (Supple- mentary 3.2)
Worst post- dose observation carried forward after Day 1 (Visit 3)	Worst post-dose observation carried forward	Worst post-dose observation carried forward	C_5.1 (Supple- mentary 4.1)
Last observation carried forward after Day 1 (Visit 3)	Last observation carried forward	Last observation carried forward	C_5.2 (Supple- mentary 4.2)
Values set to missing after Day 1 (Visit 3), no imputation	Values set to missing after SoC, no imputation	No imputation	C_5.3* (Supple- mentary 4.3)
Multiple imputation using linear regression after Day 1 (visit 3)	Multiple imputation using linear regression	Multiple imputation using linear regression	C_5.4 (Supple- mentary 4.4)

* Analyses will be performed with a mixed effect repeated measurement model as described in Section 4.4.2. All other analyses will be performed with an ANCOVA model as described above.

For the other continuous endpoints, i. e. absolute change of BSA affected by AD and percent change of the weekly average of the Peak Pruritus 0-10 NRS score from baseline at Day 84 (Visit 7) the same analyses as described above will be performed.

After applying multiple imputation using linear regression the imputed values will be restricted to the following ranges by setting values below the minimum to the minimum and values above the maximum to the maximum possible value:

- BSA affected by AD: 0 100 %,
- Peak Pruritus 0-10 NRS: 0 10.

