3.1 Objectives and Endpoints

Objectives	Endpoints			
 Primary objective To assess the efficacy of zabedosertib vs. placebo in adult patients with moderate-to-severe atopic dermatitis (AD) with inadequate response to topical corticosteroids or if topical treatments are medically not advisable 	 Primary endpoint: Achievement of 75% reduction from baseline in the Eczema Area and Severity Index (EASI 75 response) at Week 12 (Day 84) Primary endpoint (see Section 3.2) is the composite variable defined as follows: an EASI 75 response at Week 12 (Day 84), no stop of study intervention for reasons related to lack of efficacy, no rescue medication use during the 4 weeks before Day 84 and no use of systemic AD treatment. 			
	 Secondary endpoints: Percent change from baseline in EASI at Week 12 (Day 84) Achievement of EASI 50 response at Week 12 (Day 84) Achievement of EASI 90 response at Week 12 (Day 84) Achievement of a vIGA-AD response (score 0 or 1 and ≥ 2 points improvement) at Week 12 (Day 84) Absolute change from baseline in body surface area (BSA) affected by AD at Week 12 (Day 84) Absolute values and percent change of the weekly average of the Peak Pruritus 0-10 NRS score from baseline at Week 12 (Day 84) Achievement of a ≥ 4 point-improvement (reduction) in the weekly average of the Peak Pruritus 0-10 NRS score from baseline at Week 12 (Day 84) for participants with Peak Pruritus 0-10 NRS score ≥ 4 at baseline 			

Clinical Study Protocol Amendment 1 BAY 1834845 / 22158

Page: 24 of 93

Objectives	Endpoints
Secondary objectives	
 To assess the safety and tolerability of zabedosertib vs. placebo 	 Secondary endpoints: Frequency and severity of TEAEs Other safety endpoints: Frequency and severity of TEAEs of special interest Changes in vital signs from baseline Changes in clinical laboratory test results from baseline (e.g., chemistry lipid panel, hematology, urinalyses) Changes in ECG parameters from baseline and frequency of ECG findings
Other pre-specified / Exploratory objectives	Other Pre-Specified Endpoints
• To further assess the efficacy of zabedosertib vs. placebo	 Achievement of EASI 75 response up to Week 8 (Day 56) Achievement of EASI 100 response at Week 12 (Day 84) Achievement of a ≥ 3 point- improvement (reduction) in the weekly average of the Peak Pruritus 0-10 NRS from baseline at Week 12 (Day 84)
	 Absolute values and percent change from baseline in weekly averages of Peak Pruritus 0-10 NRS scores over time

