8.4 Handling of efficacy data (ClinRO and PRO) and imputation strategy

8.4.1 Data handling and visit windows for analysis

After occurrence of an intercurrent event (such as use of rescue medication or systemic SoC) the analysis will be performed according to the estimands. Data collected after use of topical rescue medication or systemic SoC are likely to show improvement in efficacy assessments. Such favourable values should not be included for analysis (unless stated otherwise, i.e. for the analysis of the effect of study intervention and rescue medication combined).

Therefore, the following first data handling step will be performed for participants who use systemic SoC or who use topical rescue medication at or after Day 56 (Visit 6) (or Day x (Visit x) for supplementary analyses):

All efficacy assessments (ClinRO or PRO) collected after (i.e. on the next day or later) first start of systemic SoC or start of topical rescue medication at or after Day 56 (Visit 6) (or Day x (Visit x) for supplementary analyses) will be set to missing (including FU visit). In case of use of rescue medication at Day 56 (Visit 6) (or Day x (Visit x) for supplementary analyses) which already started before that day the assessments after start of rescue medication will be set to missing as well.

This refers to use of any medication from the systemic SoC list and topical rescue medication list in Section 8.3 no matter if the medication was adjudicated as intercurrent event "use of systemic SoC" / "use of rescue medication at or after Day 56 (Visit 6)" as described in Section 8.3 or not.

Then the following data handling steps will be performed for all participants:

Efficacy assessments (i. e. ClinRO and ePRO weekly average of Peak Pruritus 0-10 NRS) at planned visits will be considered valid for analysis if they fall in the following visit windows (for Peak Pruritus the assessments at the actual visit days will be checked):

Day 1 (Visit 3)	Day 1*
Day 14 (Visit 4)	[Day 10, Day 18]
Day 28 (Visit 5)	[Day 21, Day 35]
Day 56 (Visit 6)	[Day 49, Day 63]
Day 84 (Visit 7)	[Day 76, Day 92]
FU (Visit 8)	no restriction

Table 8-3: Visit windows for analysis

* If the efficacy assessment is done at Day 1 (Visit 3) but treatment is started later, the assessment will also be acceptable.

[figure not shown]

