Likewise, valid values from end of treatment visits and unscheduled visits can be assigned to the respective planned visits if they fall into the visit window as listed above. If several assessments fall into the same visit window the one closer to the planned visit day will be taken unless rescue medication was taken before at least one of the assessments. If there is still an assessment(s) without prior rescue medication use the one closest to the planned visit day will be selected. Otherwise, the one with greater distance to prior rescue medication use will be selected. (If there should be two assessments with equal distance to the planned visit date and not affected by rescue medication use then the one assessed at the regular visit will be taken.) Assessments from end of treatment visits after early discontinuation of study drug will only be considered for assignment to a planned visit if the end of treatment visit was not later than three days after last study drug intake.

[figure not shown]
Especially, it will be checked according to the criteria specified above if data from an early discontinuation visit or unscheduled visit before the use of rescue medication at Day 56 (Visit 6) (or Day x (Visit x) for supplementary analyses) or use of systemic SoC is available which fulfills the rules defined above. Likewise, in case of early discontinuation due to lack of efficacy or due to other reasons it will be checked if data from an early discontinuation visit or unscheduled visit before the intercurrent event is available which fulfills the rules defined above. If so, these values will be assigned to the respective planned visit.

Imputation of efficacy data for visits after an intercurrent event will be described in Section 8.4.2 and 8.4.3.

Note that events of "use of topical rescue medication" and "use of systemic standard of care" which are not considered intercurrent events as described in Section 8.3 (i. e. if the medication was not used for treatment of AD) will be handled and imputed as described for the intercurrent event "discontinuation of study intervention due to other reasons" (refer to Section 8.3).

[figure not shown]

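### A Day 84 itch score recorded in the daily diary can be set to missing and imputed, because the SAP derives it only through a clinic visit in the analysis window

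*SAP*

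**What the plan says.** Protocol 8.2.2 has the Peak Pruritus NRS entered daily on a handheld device at home for the whole study. SAP 4.3.2 turns this diary into a weekly average that is "evaluated in a visit-based manner, in order to enable an analysis comparable to the ClinROs". The rule is "The daily Peak Pruritus score at the 7 days preceding the visit will be averaged (arithmetic mean) if at least 4 scores are present". If that condition fails, "Otherwise, the weekly Peak Pruritus 0-10 NRS will be missing for the respective visit". A further restriction applies at the end of dosing: "For end of treatment visits no scores after end of treatment will be considered for the average".

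SAP 8.4.1 decides which visits count. The weekly itch average is valid for a planned visit only if the visit falls in the Table 8-3 window, and "for Peak Pruritus the assessments at the actual visit days will be checked". For Visit 7 the window is Day 76 to Day 92. There is a substitution rule: "valid values from end of treatment visits and unscheduled visits can be assigned to the respective planned visits", provided they fall in the window. An end-of-treatment visit after early discontinuation qualifies only if it took place within three days of last intake.

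The follow-up visit is the exception. After a technical fault in the diary recording, "it will be based on the recording from Day 17 to Day 23 after end of treatment for all participants".

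No readable rule derives a Day 84 average from the diary when no qualifying visit exists. The text after SAP 8.4.1, where the contents list places the detailed imputation rules (8.4.2 and 8.4.3), is blacked out in the public version.

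**The concern.** The diary runs whether or not the participant attends. A Week 12 itch outcome can therefore be fully recorded while the plan treats it as missing. EASI, vIGA-AD and BSA cannot be known without a visit; itch can.

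Such a participant can stay in the main analysis, because the per protocol set (SAP 3) asks for an EASI score at Day 56 or later, not specifically at Day 84. The missing itch value is then filled in:

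- For the response of at least 4 points, by logistic-regression multiple imputation in the main analysis, and by non-response or last observation carried forward in the sensitivity analyses (SAP 4.2.2, 4.2.3 and 4.3.2).
- For percent change, by linear-regression multiple imputation, worst post-dose value or last observation carried forward (SAP 4.3.2).

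The exploratory response of at least 3 points and the over-time itch endpoint use the same averages. A missed Visit 6 also removes the Day 56 itch average that the imputation model uses as a predictor. At stake is the replacement of observed outcomes by modelled ones in a small trial.

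**Working it through.** The plan gives no figure for itch. Its only design figure, at least 90% power for EASI 75 with 38 and 19 evaluable participants, reproduces (exact enumeration 0.910) and does not bear on this point.

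**Inputs**
- Average over the 7 days before the visit, at least 4 scores, none after end of treatment (SAP 4.3.2).
- Visit 7 analysis window Day 76 to Day 92 (SAP 8.4.1, Table 8-3); scheduling window Day 84 ±3 (Protocol 1.3).
- 38 and 19 evaluable participants (SAP 5).

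**Step 1: which days are averaged.** A visit on Day v uses Days v−7 to v−1. A Day 84 visit uses Days 77 to 83.

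**Step 2: no qualifying visit.** If Visit 7 is missed or falls after Day 92, and no end-of-treatment or unscheduled visit lies in Days 76 to 92, no average is formed. A complete diary then contributes 0 of its 7 scores from Days 77 to 83.

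**Step 3: truncation at end of treatment.** Let the last dose be on Day L and the end-of-treatment visit on Day v, with gap g = v − L. With a complete diary the usable scores number 8 − g, capped at 7 and not below 0. Assuming L = 84:

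| Visit day | g | Usable scores | Result |
|---|---|---|---|
| 85 | 1 | 7 | average |
| 87 | 3 | 5 | average |
| 88 | 4 | 4 | average |
| 89 | 5 | 3 | missing |
| 92 | 8 | 0 | missing |

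Visits on Days 89 to 92 are inside the analysis window and still give no value. For early stoppers the three-day rule limits g to 3, which leaves at least 5 scores. Truncation alone therefore affects participants who finish the course and attend late.

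**Step 4: weight of one participant.** In the sensitivity analysis that imputes non-response, one itch responder lost this way lowers the response rate by 1/38 = 2.6 percentage points on zabedosertib or 1/19 = 5.3 points on placebo.

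**Step 5: what a fallback recovers.** In Step 2, averaging Days 77 to 83 uses all 7 scores. In Step 3 with L = 84, the 7 days up to last dose are Days 78 to 84, again 7 scores.

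**Step 6: would fixed days for everyone be better?** Under the Protocol 1.3 schedule, dosing runs to Visit 7. Take a fixed week of Days 78 to 84, limited to scores up to last dose. A compliant Day 81 visit leaves Days 78 to 81, at most 4 scores. A visit on Day 80, inside the SAP window, leaves 3, so the value is always missing. The current rule offers 7 days in both cases.

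**The case against.** The strongest defence is that visit anchoring is a stated, deliberate choice with merits. It aligns itch with EASI and BSA for the planned correlations (SAP 4.4.5), mirrors the baseline average over the 7 days before randomization, and adapts to a variable end of dosing, as Step 6 shows. That stands, and it is why the main rule should stay. It does not cover the cases here: where no qualifying visit exists, there is no ClinRO value to be comparable with.

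The substitution rule and the 17-day window also make the loss uncommon, and the protocol schedule makes a gap of five or more days between last dose and Visit 7 unusual. Both limit the size of the problem without removing it.

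A reader might infer more, but the documents do not support it:

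- *That Week 12 is an unacceptably different week for different people.* Visits on Days 81 and 87 do average Days 74 to 80 and 80 to 86, and the SAP limits give Days 69 to 75 and 85 to 91. But the ClinROs use the same windows, and Days 76 and 92 both lie outside the protocol's ±3 days.
- *That two thirds of the diary is lost, because 8 of 12 weeks enter no model.* The secondary itch endpoints are defined at Week 12 only. The protocol's exploratory endpoint, "Absolute values and percent change from baseline in weekly averages of Peak Pruritus 0-10 NRS scores over time", does not call for 12 modelled weeks; Protocol 9.3.5 assigns exploratory endpoints to descriptive statistics, and SAP 4.4.5 plots the daily scores. An unstructured covariance for 12 weeks has 12 × 13 / 2 = 78 parameters, against 4 × 5 / 2 = 10 for four visits, with about 57 participants.
- *That the follow-up rule is a precedent for fixed days throughout.* It was forced by a technical fault, and follow-up efficacy is only summarised (SAP 4.1.1). It shows that a fixed-day average is feasible, no more.

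**Conclusion.** The point holds as a limited gap. On the readable text, a measured on-treatment Day 84 itch outcome can become missing and be imputed in two situations: no qualifying visit in Days 76 to 92, or an in-window end-of-treatment visit so long after last dose that fewer than 4 scores remain.

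The count cannot be derived, because the documents give no rate of missed or late visits. An assumed 3% to 8% of 57 would be 1.7 to 4.6 participants. Reading that as 2 to 5 lost outcomes would be a ceiling, because it supposes that every missed visit comes with a usable on-treatment diary; participants who stopped drug earlier have none. The true number is probably small.

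The itch endpoints concerned are supportive secondary or exploratory. SAP 4.3.1 names no key secondary endpoints, and the EASI 75 success criterion is unaffected. The conclusion assumes that the blacked-out parts of SAP 8.4 contain no diary fallback. One there cannot be excluded, though SAP 4.3.2 and 8.4.1 point to none.

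**What to change.** Keep the visit-anchored average as the main rule and add a fallback to SAP 4.3.2:

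- Where no valid visit-based average exists for a planned on-treatment visit, average the on-treatment daily scores of the 7 days before the planned visit day: Days 7 to 13, 21 to 27, 49 to 55 and 77 to 83 for Days 14, 28, 56 and 84.
- Where truncation at end of treatment caused the loss and last dose lies in the visit window, use the 7 days up to last dose instead.
- In both cases require at least 4 scores, and use only scores before any rescue medication or SoC that censors efficacy data in that analysis.

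Report how many values come from the fallback, by arm. If the blacked-out text already contains such a rule, a cross-reference in SAP 4.3.2 is enough. A descriptive summary of all 12 weekly averages is optional.

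The cost is a short addition to the SAP and some programming on data already collected. The small downside is that, for these few participants, the itch week is not tied to a ClinRO visit. The change should be settled before unblinding. If results from the administrative interim analysis (SAP 4.7) already exist, label the analysis with the fallback as supplementary.
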